4. ANALYSIS POPULATIONS

Population	Definition / Criteria	Analyses Evaluated
Screened	All participants who were screened for eligibility.	Study Population
Enrolled	All randomised participants.	Study Population
Safety	All randomised participants who received at least one dose of blinded study treatment. If participants receive a treatment different to their randomized treatment, they will be	Study Population Safety

Population	Definition / Criteria	Analyses Evaluated
	analysed according to the treatment actually received.	
Safety Open Label, PQ phase, Non-Relapsers (Safety OL)	All participants in the safety population who did not relapse during the double-blind phase and went onto the open-label primaquine phase at the end of the study.	Study Population Safety
Microbiologic-Intent-To-Treat (mITT)	All randomized participants who received at least one dose of blinded study treatment and have microscopically-confirmed P. vivax parasitaemia at baseline. Participants will be analysed according to their randomized treatment.	Efficacy
Per-Protocol (PP)	All participants in the mITT population for whom there were no major protocol deviations that impact the primary endpoint. Protocol deviations that would exclude participants from the PP population are defined in Section 4.1 (Protocol Deviations) and Appendix 1 (Protocol Deviation Management and Definition for Per-Protocol Population).	Sensitivity/ supporting analyses of efficacy data
PK population	All participants for whom at least one systemic tafenoquine concentration, and associated sample date/time is available.	PK

NOTES:

Please refer to [Appendix 11](#): List of Data Displays which details the population to be used for each display being generated.

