11.3. Appendix 3: Assessment Windows

11.3.1. Definitions of Assessment Windows for Analyses

Analysis Set / Domain	Parameter (if applicable)	Target	Analysis Window		Analysis Timepoint
			Beginning Timepoint	Ending Timepoint	
miTT, PP, Safety	All	Day 1	Day 1	Day 1	Day 1
miTT, PP, Safety	All	Day 2	Day 2	Day 2	Day 2
miTT, PP, Safety	All	Day 3	Day 3	Day 3	Day 3
Safety	ECG	4 hours after last DHA-PQP dose	3 hours after last DHA-PQP dose	6 hours after last DHA-PQP dose	4 hours after last DHA-PQP dose
miTT, PP, Safety	All	Day 4	Day 4	Day 4	Day 4
miTT, PP, Safety	All	Day 5	Day 5	Day 5	Day 5
miTT, PP, Safety	All	Day 6	Day 6	Day 6	Day 6
miTT, PP, Safety	All	Day 7	Day 7	Day 7	Day 7
miTT, PP, Safety	All	Day 8	Day 8	Day 8	Day 8
miTT, PP, Safety	All	Day 9	Day 9	Day 9	Day 9
miTT, PP, Safety	All	Day 10	Day 10	Day 10	Day 10
miTT, PP, Safety	MetHB	Day 11	Day 11	Day 11	Day 11
miTT, PP, Safety	MetHB	Day 12	Day 12	Day 12	Day 12
miTT, PP, Safety	MetHB	Day 13	Day 13	Day 13	Day 13
miTT, PP, Safety	MetHB	Day 14	Day 14	Day 17	Day 14
miTT, PP, Safety	All except MetHB	Day 14	Day 11	Day 17	Day 14
miTT, PP, Safety	All	Day 21	Day 18	Day 24	Day 21
miTT, PP, Safety	All	Day 28	Day 25	Day 43	Day 28
miTT, PP, Safety	All	Day 60	Day 44	Day 75	Day 60
miTT, PP, Safety	All	Day 90	Day 76	Day 105	Day 90
miTT, PP, Safety	All	Day 120	Day 106	Day 135	Day 120
miTT, PP, Safety	All	Day 150	Day 136	Day 169	Day 150
miTT, PP, Safety	All	Day 180	Day 170	Day 190	Day 180
Safety OL	All	Day 180 visit + 15-21 days	Day 180 visit + 15 days	Day 180 visit + 21 days	Day 195

Note: Data collected after the nominal day 180 study visit, i.e. after the start of open label PQ for non-relapsers, will not be slotted to any visit up to and including the day 180 visit, regardless of the study day. Only the Day 195 visit window will be considered for slotting.

For all data summarised by visit, the nominal visit description will be used. Unscheduled and withdrawal visit data will be slotted into a scheduled visit window, but the data will only be included in summaries and figures if no scheduled visit exists within the same window. If there are multiple assessments within the same window which are not unscheduled visits, the earliest result will be used in the summaries and figures. If only unscheduled visits are included in the same window, the earliest of these results will be used in summaries and figures.

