11.6.3. Efficacy**Efficacy endpoints****Relapse free efficacy at six months**

Relapse is defined as any recurrence of *P. vivax* malaria after clearance of the initial infection.

Participants will be considered to have demonstrated relapse-free efficacy at six months if all of the following are true (also described in [Figure 1](#)):

Participant had a non-zero *P. vivax* asexual parasite count at baseline. Participants who do not meet this criterion will be censored, with time to relapse censored at 0 days.

Participant demonstrated initial clearance of *P. vivax* parasitemia. This is defined as two negative asexual *P. vivax* parasite counts, with at least 6 hours between the counts, and no positive counts in the interval. Participants who do not meet this criterion will be censored with time to relapse censored at 0 days.

Participant has no positive asexual *P. vivax* parasite count at any assessment prior to or on Day 180 visit following initial parasite clearance. Participants who do have a positive count will be considered to have relapsed with time to relapse = (date of first positive count) – (date of Study Day 1) days.

Participants did not take a concomitant medication with anti-malarial activity (excluding study treatment) at any point between Study Day 1 and their last parasite assessment. Participants who did take a drug with anti-malarial activity but never had a positive asexual *P. vivax* parasite count after initial clearance will be censored with time to relapse censored at (date of last negative parasite assessment prior to concomitant medication start) – (date of Study Day 1) days. If a participant has not had a negative assessment prior to the concomitant medication start date, they will be censored at 0 days.

[figure not shown]
Efficacy endpoints

Participant is parasite-free at 6 months. This is defined as a negative asexual *P. vivax* parasite count at the first parasite assessment performed on or after Study Day 170.

Participants who do not have a Day 180 visit and have not already failed or been censored will be censored at (date of final parasite assessment) – (date of Study Day 1) days).

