If a participant has a relapse outcome and a censored outcome, they will be considered to be a relapse, even if the time point of the relapse is later than the time point of censoring. For example, a participant who took a medication with anti-malarial activity at Study Day 32, but remained parasite-free after initial clearance until Study Day 68 will be treated as a relapse at Study Day 68.

Figure 1 Flowchart of algorithm for relapse-free efficacy at 6 months

Relapse free efficacy at four months

Relapse is defined as any recurrence of *P. vivax* malaria after clearance of the initial infection.

Participants will be considered to have demonstrated relapse-free efficacy at four months if all of the following are true (also described in [Figure 2](#)):

Participant had a non-zero *P. vivax* asexual parasite count at baseline. Participants who do not meet this criterion will be censored, with time to relapse censored at 0 days.

Participant demonstrated initial clearance of *P. vivax* parasitemia. This is defined as two negative asexual *P. vivax* parasite counts, with at least 6 hours between the counts, and no positive counts in the interval. Participants who do not meet this criterion will be censored with time to relapse censored at 0 days.

Participant has no positive asexual *P. vivax* parasite count at any assessment prior to or on

Efficacy endpoints

Study Day 135 following initial parasite clearance. Participants who do have a positive count will be considered to have relapsed with time to relapse = (date of first positive count) – (date of Study Day 1) days.

[figure not shown]
Participants did not take a concomitant medication with anti-malarial activity (excluding study treatment) at any point between Study Day 1 and their first parasite assessment after Study Day 105 (up to and including Study Day 135). Participants who did take a drug with anti-malarial activity but never had a positive asexual *P. vivax* parasite count after initial clearance will be censored with time to relapse censored at (date of last negative parasite assessment prior to concomitant medication start) – (date of Study Day 1) days. If a participant has not had a negative assessment prior to the concomitant medication start date, they will be censored at 0 days.

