Participant is parasite-free at 4 months. This is defined as a negative asexual *P. vivax* parasite count at the first parasite assessment performed on or after Study Day 105 (up to and including Study Day 135).

Participants who do not have a Day 120 visit and have not already failed or been censored will be censored at (date of final parasite assessment prior to Day 120) – (date of Study Day 1) days.

If a participant has a relapse outcome and a censored outcome, they will be considered to be a relapse, even if the time point of the relapse is later than the time point of censoring. For example, a participant who took a medication with anti-malarial activity at Study Day 32, but remained parasite-free after initial clearance until Study Day 68 will be treated as a relapse at Study Day 68.

Figure 2 Flowchart of algorithm for relapse-free efficacy at 4 months

Efficacy endpoints
Relapse free efficacy at 6 months missing=failure definition

In addition to those with a positive asexual P. vivax parasite count at any assessment prior to or on Study Day 190, the following participants will also be defined to have relapsed:
 
Participant did not demonstrate initial clearance of P. vivax parasitaemia (i.e. did not have two negative asexual P. vivax parasite counts, with at least 6 hours between the counts, and no positive counts in the interval)
 
Participant took a concomitant medication with anti-malarial activity at any point between Study Day 1 and their last parasite assessment. A list of all concomitant medications will be reviewed by a GSK clinician prior to unblinding the study, and classified accordingly.
 
Participant does not have a parasite assessment between Study Day 170 and 190.
 
Participants with a zero P. vivax asexual parasite count at baseline will be excluded from the analysis.

Genetic classification of relapse (heterologous/homologous)

Relapse-free efficacy at 6 months will be assessed separately according to whether the first P. vivax re-infection is homologous or heterologous to the original infection. The definition is as detailed above but heterologous infections will be censored at the time at which they occur for the endpoint looking at homologous infections only; and homologous infections will be censored at the time at which they occur for the endpoint looking at heterologous infections only.

Recrudescence

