
A participant will be considered to have had a recrudescence if the following are true:
 
Included in mITT population
 
Participant had a positive P. vivax asexual parasite count at baseline and demonstrates clearance (i.e. two negative asexual P. vivax parasite counts, with at least 6 hours between the counts, and no positive counts in the interval).
 
Participant has a positive genetically homologous asexual P. vivax parasite count on or before Study Day 14, after their zero count in days 1 to 5.
 
The following participants will have a censored time to recrudescence of 0 days:
 
Participant had no asexual P. vivax parasites at baseline.
 
Participant had a positive P. vivax asexual parasite count at baseline but had no subsequent zero asexual parasite count within study Days 1-5.
 
If a participant does not meet the definition of recrudescence, but took a concomitant medication with anti-malarial activity between Study Day 1 and Study Day 14, they will be censored, with time to recrudescence censored at (date of last negative parasite assessment prior to concomitant medication start) – (date of Study Day 1). If a participant has not had a negative assessment prior to the concomitant medication start date, they will be censored at 0 days.
 
All other participants will be censored with time to recrudescence censored at their last parasite assessment on or before Study Day 14, with time to recrudescence = (date of final parasite assessment) – (date of Study Day 1).

Number of Relapses

A participant is considered to have had at least one relapse if they:
 
demonstrated initial clearance of P. vivax parasitemia (defined as two negative asexual P.

Number of Relapses

vivax parasite counts, with at least 6 hours between the counts, and no positive counts in the interval)
 
subsequently had a positive asexual P. vivax parasite count at any assessment up to and including their Day 180 visit.
 
A participant is considered to have had a subsequent relapse if they:
 
demonstrated clearance of P. vivax parasitemia following their previous relapse (defined as a negative asexual P. vivax parasite count)
 
subsequently had a positive asexual P. vivax parasite count at any assessment up to and including their Day 180 visit.

Clearance time
Parasite (PCT)

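### The missing=failure relapse rule (SAP 11.6.3, Table 2.12) omits the post-clearance condition and runs to Study Day 190, so it does not match the primary relapse definition

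*SAP*

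**What the plan says.** The missing=failure version of six-month relapse-free efficacy has its own derivation in SAP 11.6.3. It feeds Table 2.12, a logistic regression on battalion and treatment (SAP 7.1.5.1). A man has relapsed if he has a positive asexual "parasite count at any assessment prior to or on Study Day 190, the following participants will also be defined to have relapsed". Three further groups are added as failures: no demonstrated initial clearance, use of a concomitant antimalarial, and no smear between Study Days 170 and 190. Men with a zero asexual count at baseline are left out.

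The neighbouring rules read differently:

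- **Primary six-month rule (SAP 11.6.3):** a positive "parasite count at any assessment prior to or on Day 180 visit following initial parasite clearance".
- **Four-month rule (SAP 11.6.3):** positives up to "Study Day 135 following initial parasite clearance".
- **Number of relapses (SAP 11.6.3):** clearance first, then a positive "parasite count at any assessment up to and including their Day 180 visit".
- **Protocol 9.4:** nothing later than the Day 180 visit is used for six-month relapse.
- **SAP 11.3.1, note:** data collected "after the start of open label PQ for non-relapsers, will not be slotted to any visit up to and including the day 180 visit".

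The mITT population is "All randomized participants who received at least one dose of blinded study treatment and have microscopically-confirmed" *P. vivax* parasitaemia at baseline (SAP 4). On antimalarials, the primary rule requires that "Participants did not take a concomitant medication with anti-malarial activity (excluding study treatment) at any point between Study Day 1 and their last parasite assessment". The missing=failure criterion covers the same span but lacks the words in brackets.

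**The concern.** Table 2.12 carries forward the protocol's analysis in which every subject is classed as a success or a failure (Protocol 9.4.1), and it is the planned check that counts missing outcomes as failures. It is useful only if it differs from the primary analysis in how missing outcomes are handled and in nothing else. Here the event itself has been redefined. Followed word for word, the rule counts the infection that brought the man into the trial. Repaired informally, it depends on a programmer's guess at the missing condition. The later cut-off also lets in smears taken after open-label primaquine has been dispensed, so the same man could be a success in one analysis and a failure in the other for reasons unrelated to missing data.

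**Working it through.** **1. The plan's own figure.** Protocol 9.2.1 assumes 50 men per arm and relapse-free rates of 50% (control), 85% (primaquine) and 85% (tafenoquine). Expected relapses are 50 × (0.50 + 0.15 + 0.15) = 40, and 40/150 = 26.7%, as stated.

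**2. The rule as written.** mITT entry requires baseline parasitaemia, and a zero baseline asexual count removes a man from this analysis. Everyone analysed therefore has a positive pre-treatment smear. The SAP treats these smears as assessments (SAP 5.2; shells EFF_T1 and EFF_L2), and they precede Study Day 190. All are relapses: 150/150 if all have a positive count. With one outcome category, no odds ratio can be estimated.

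Four example men, coded under three rules:

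| Man | As written | After clearance, to Day 180 visit | After clearance, to Study Day 190 |
|---|---|---|---|
| Day 1 positive, all later smears negative to Day 180 | Failure | Success | Success |
| Positive on Day 60 | Failure | Failure | Failure |
| Day 180 visit on Study Day 172 negative; unscheduled positive on Study Day 186 | Failure | Success | Failure |
| Day 180 visit on Study Day 193, negative | Failure | Failure (no smear in 170-190) | Failure (no smear in 170-190) |

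The first row turns only on the clearance condition. The third turns only on the cut-off.

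**3. A post-baseline repair.** Smears are taken twice daily on Days 2-3 until two consecutive negatives (Protocol 7.1, note c). A man still positive on Day 2 who then clears normally has a post-baseline positive. He would be a relapse under that repair and not under the primary rule.

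**4. What the table should show.** With the clearance condition restored, and assuming missingness at rate d independent of relapse, the failure rate is 1 − (1 − d) × (relapse-free rate). Protocol 9.2.1 allows 10% withdrawal; the range is 0 to 10%.

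| d | Control | Each active arm | Failures in 150 | Odds ratio, tafenoquine v control |
|---|---|---|---|---|
| 0% | 50.0% | 15.0% | 40.0 (26.7%) | 0.176 |
| 5% | 52.5% | 19.3% | 45.5 (30.3%) | 0.216 |
| 10% | 55.0% | 23.5% | 51.0 (34.0%) | 0.251 |

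**5. The cut-off.** The Day 180 window is ±10 days, so an in-window visit can fall on Study Day 170, leaving 190 − 170 = 20 later days that count here and not in the primary rule. One man moved is 1/50 = 2 points in his arm. From the 10% row, one tafenoquine man moved gives 23.5% + 2% = 25.5% and an odds ratio of (0.255/0.745)/(0.55/0.45) = 0.280. One control man moved gives 57% and (0.235/0.765)/(0.57/0.43) = 0.232. The men who could move are the non-relapsing completers: 50 × 0.9 × 0.85 = 38.25 on tafenoquine and 50 × 0.9 × 0.50 = 22.5 on control. The documents do not give the number of such smears.

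**6. The antimalarial criterion.** Open-label primaquine goes only to men who have not relapsed, is recorded in the eCRF (Protocol 6.8), and is absent from the study treatment table (Protocol 6). The SAP's definition of a concomitant medication has no upper date (SAP 11.4.1.1). If such a man has any later smear, his last parasite assessment falls after an antimalarial. The primary rule would censor him at his last negative smear before the drug, ordinarily the Day 180 visit, so little is lost. Here he would become a failure.

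**The case against.** The strongest reply is that nobody would program the literal rule. SAP 2.2 and the opening of the primary definition in 11.6.3 make relapse a recurrence after clearance. The separate criterion for failure to clear would be redundant if the baseline smear already counted. The Table 2.12 footnotes list the added failures and baseline positivity is not among them. SAP 7.1.5.1 asks for counts of relapse-free men, and shell EFF_L1 shows a success on this endpoint. This stands as evidence of intent. A reader might infer that Table 2.12 will come out with every man failed and no estimable odds ratio; the documents do not support that as a forecast. It remains true that the operative sentence lacks the condition and that the obvious short repair is wrong (step 3).

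On the cut-off, Study Day 190 is the upper edge of the Day 180 window, matches the 170-190 criterion beside it, and gives a date for men with no Day 180 visit. No smear is scheduled after the Day 180 visit, and none at Day 195. This stands, and it means few men are likely to be affected. It does not reconcile the rule with Protocol 9.4 or the primary definition. The note in SAP 11.3.1 governs slotting to visits, while this event rule works by study day.

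On antimalarials, a clinician classifies all concomitant medications before unblinding, which may remove the problem in practice. Nor is the span to the last parasite assessment a departure from the primary rule: both use it. The differences are the missing bracketed words and the consequence, failure instead of censoring. The bracketed words alone would not clearly cover open-label primaquine.

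**Conclusion.** The point holds as two mismatches with the primary relapse definition and one lesser gap, all in a sensitivity analysis.

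- **Clearance condition.** Its absence is an error in a stated rule. The literal consequence is 100% failures; the intended result, under the planning rates with 10% independent missingness, is about 34.0%.
- **Study Day 190.** This is a smaller inconsistency, worth 2 percentage points of an arm per man affected, with an unknown and probably small number of men.
- **Antimalarial criterion.** It leaves the status of open-label primaquine unclear when a later smear exists.

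A reader might infer a bias against tafenoquine, because only men relapse-free at Day 180 can be reclassified and more of them are expected on tafenoquine. That is not established. The pools differ by a factor of 38.25/22.5 = 1.7, but the cut-off needs a positive smear, and control non-relapsers have had no anti-hypnozoite drug before Day 180. If their risk per man were more than 1.7 times as high, more control men would move. The documents give no such risk. Nor do the clearance and cut-off points touch the primary Cox analysis (Table 2.8), which uses its own rule.

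**What to change.** In the missing=failure derivation, define the event as a positive asexual *P. vivax* count at any smear after initial clearance has been shown, up to and including the man's Day 180 visit, or up to Study Day 190 if he has no Day 180 visit. The primary rule's phrase "prior to or on Day 180 visit following initial parasite clearance" already supplies most of the wording. Keep the separate 170-190 criterion for missing smears.

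In the antimalarial criterion, state that study treatment and protocol open-label primaquine are excluded and that the period ends at the Day 180 visit. Use the same end point in the primary rule, which brings it back to Protocol 9.4, and align the Table 2.12 footnotes.

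The cost is a few lines of SAP text and the matching program specification, settled before unblinding. No new data, visits or sample size are involved.

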### **9.2 Sample Size Considerations**

#### **9.2.1 Sample Size Assumptions**

The sample size for the study is based on the comparison of the primary endpoint (i.e. relapse-free efficacy at 6 months post-dosing) between the DHA-PQP alone group versus DHA-PQP plus TQ. The comparison will be based on a Log rank test for the difference in relapse-free survival rates over 6 months using all the subjects in the intent to treat population.

It is assumed that the relapse-free efficacy will be 50% on DHA-PQP alone, 85% on DHA-PQP plus PQ, and 85% on DHA-PQP plus TQ. In order to detect a clinically meaningful difference of 35%, a sample size of 50 subjects per group will provide >90% overall power for the primary efficacy comparison, allowing for a 10% withdrawal rate. A trial of 150 subjects, with the given assumptions about DHA-PQP, DHA-PQP plus PQ, and DHA-PQP plus TQ relapse rates would expect to see 40 relapses: a combined relapse rate across all treatments of 26.7%. In addition, a DHA-PQP plus PQ arm will be used as a benchmark to help further interpret the observed relapse efficacy of DHA-PQP plus TQ.

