
By genetic classification of First P. vivax Recurrence
 
Repeat primary analysis censoring participants with homologous infections (Table 2.13) and censoring participants with heterologous infections (Table 2.14), present: Number of participants with an observed relapse and numbers of participants censored

Primary Statistical Analyses
Kaplan-Meier estimate and 95% confidence interval of the relapse-free efficacy rate at 6 months for each treatment. Kaplan-Meier quartile estimates and 95% confidence intervals of time to relapse Kaplan-Meier survival curves will also be produced (Figure 2.3 and Figure 2.4).

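### In the supportive analyses by genetic type, the other type of first recurrence is censored although it competes, so Kaplan-Meier overstates type-specific relapse where the two types overlap in time, more so in the control arm.

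*SAP*

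**What the plan says.** SAP 11.6.3 (genetic classification of relapse) assesses 6-month relapse-free efficacy separately by the type of the first recurrence. For one endpoint "heterologous infections will be censored at the time at which they occur for the endpoint looking at homologous infections only"; for the other, "homologous infections will be censored at the time at which they occur for the endpoint looking at heterologous infections only". SAP 7.1.5.1 lists the work among the sensitivity and supportive analyses: "Repeat primary analysis censoring participants with homologous infections (Table 2.13) and censoring participants with heterologous infections (Table 2.14"). It asks for the numbers observed to relapse and censored, the "Kaplan-Meier estimate and 95% confidence interval of the relapse-free efficacy rate at 6 months for each treatment", Kaplan-Meier quartiles of time to relapse, and curves (Figures 2.3 and 2.4).

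SAP 11.11.2 assigns mock shell TTE1 to both tables and adds titles and footnotes stating that the other type is censored when it occurs. TTE1 also carries a crude n (%) row of subjects observed to relapse, hazard ratios, and a number needed to treat.

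Neither document mentions competing risks or cumulative incidence.

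**The concern.** A first recurrence is either homologous or heterologous. It leads to rescue treatment (Protocol 6.9.1.2), and parasite genotyping is done at the first recurrence (Protocol 7.4, parasite genotyping). A participant whose first recurrence is heterologous can no longer have a homologous first recurrence. Kaplan-Meier treats that participant as censored but still able to have one, and so estimates risk in a setting where the other type never occurs.

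This censoring is valid for a cause-specific hazard ratio. It does not give the probability of a first relapse of that type, which is how a reader will take a 6-month rate, a quartile or a curve. The excess grows with the overall relapse rate, so it is larger on DHA-PQP alone than on TQ or PQ. The complements of the two type-specific rates can add up to more than the all-recurrence relapse rate in Table 2.8. If the TTE1 number-needed-to-treat row is kept and taken from these rates, it carries the same bias.

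**Working it through.** **Inputs.** Protocol 9.2.1 assumes that "relapse-free efficacy will be 50% on DHA-PQP alone, 85% on DHA-PQP plus PQ, and 85% on DHA-PQP plus TQ", so 6-month relapse F is 0.50 on control and 0.15 on TQ or PQ. There are 50 participants per arm and 10% withdrawal. The homologous share f is not in the documents; it is assumed and varied from 10% to 90%.

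**Plan's own figures first.** Expected relapses: 50 × (0.50 + 0.15 + 0.15) = 40, and 40/150 = 26.7%. This matches the protocol, which "would expect to see 40 relapses: a combined relapse rate across all treatments of 26.7" percent. For power, 45 per arm after withdrawal gives 45 × (0.50 + 0.15) = 29.25 events, and HR = ln 0.85 / ln 0.50 = 0.2345. Power is 91.8% (Freedman), 95.6% (two proportions) or 97.5% (Schoenfeld), all consistent with the stated figure of more than 90%. The documents state no figure by genetic type.

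**Formulas, with proportional type-specific hazards.**

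- Planned estimate: 1 − KM = 1 − (1 − F)^f
- Cumulative incidence of a first relapse of that type: f × F

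At f = 0.5:

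- Control: 1 − 0.50^0.5 = 29.3% against 0.5 × 50% = 25.0%. On the displayed scale this is 70.7% relapse-free against 75.0%.
- TQ or PQ: 1 − 0.85^0.5 = 7.8% against 0.5 × 15% = 7.5%.
- The two types sum to 58.6% in control against a true 50%, and to 15.6% against 15% on TQ.

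| Homologous share | Control 1 − KM | Control cum. inc. | Excess | TQ/PQ 1 − KM | TQ/PQ cum. inc. | Excess |
|---|---|---|---|---|---|---|
| 10% | 6.7 | 5.0 | 1.7 | 1.6 | 1.5 | 0.1 |
| 30% | 18.8 | 15.0 | 3.8 | 4.8 | 4.5 | 0.3 |
| 50% | 29.3 | 25.0 | 4.3 | 7.8 | 7.5 | 0.3 |
| 70% | 38.4 | 35.0 | 3.4 | 10.8 | 10.5 | 0.3 |
| 90% | 46.4 | 45.0 | 1.4 | 13.6 | 13.5 | 0.1 |

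Figures are percentages, and excesses are percentage points from unrounded values. The 4.3 points near an even split is the largest control excess under this model.

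**Quartiles.** With constant hazards and f = 0.5, the Kaplan-Meier first quartile in control falls at 180 × ln(1/0.75) / (0.5 × ln 2) = day 149. The cumulative incidence reaches 25% only at day 180.

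**Simulation check.** This used 4,000 trials with 50 per arm, 10% withdrawal and an even split.

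- Exact relapse times: 29.5% against 25.2% in control (+4.3) and 7.8% against 7.5% on TQ (+0.3).
- Relapse seen only at scheduled follow-up visits: 28.6% against 25.0% (+3.6) and 7.8% against 7.6% (+0.3).

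**If the types do not overlap in time.** The type that comes wholly first is not overstated. With an even split, the later type is overstated by 0.25/0.75 − 0.25 = 8.3 points in control and by 0.075/0.925 − 0.075 = 0.6 points on TQ.

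**The case against.** The best reply has four parts.

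- **The crude proportion is already shown.** TTE1 gives n (%) observed to relapse, which in these tables is the crude proportion with a first relapse of that type. This stands as a partial safeguard. It makes no allowance for withdrawals: with an even split and 10% withdrawal at a constant rate it would read about 23.9% in control against a cumulative incidence of 25.0%. Table 2.21 does not fill the gap, because its denominator is relapsers only (SAP 7.3.5).
- **The censoring is disclosed, and the estimates are coherent as net risks.** At an even split the two control survivals multiply back to the total, 0.707 × 0.707 = 0.50. But reading them as net risks requires the types to be independent, which these data cannot show. The hypothetical strategy in SAP 7.1.4 concerns staying on randomised medication, not removing the other relapse type.
- **The consequence is small.** These are supportive analyses for an exploratory question. At an even split they expect 50 × 0.25 = 12.5 events per type in control and 50 × 0.075 = 3.75 on TQ. A 95% interval around 25% with n = 50 has a half-width of about 12 points, well above the bias. This stands and limits the importance of the point, but imprecision is no reason to keep an estimator that targets the wrong quantity.
- **No rate difference is planned.** A reader might infer that the plan exaggerates a TQ-versus-control difference, 21.5 points instead of 17.5 at an even split. The output list in SAP 7.1.5.1 for these tables names no difference in rates, so the documents do not support that as a planned result. Only the TTE1 number needed to treat could carry it: 1/0.215 = 4.7 against 1/0.175 = 5.7.

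**Conclusion.** The point holds for the Kaplan-Meier rates, quartiles and curves in Tables 2.13 and 2.14 and Figures 2.3 and 2.4. They overstate the probability of a first relapse of a given type wherever the types overlap in time, and more so in the higher-relapse control arm. The size, 1.4 to 4.3 points in control and 0.1 to 0.3 on TQ or PQ, rests on the planned relapse rates, proportional type-specific hazards and an assumed homologous share of 10% to 90%.

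Two stronger readings are tempting. One is that both types are always inflated. The documents give neither the split nor the timing of the types, and a type that occurs wholly first is not inflated at all. The other is that the trial's main result is affected. It is not: the primary analysis counts every recurrence, and its test and power do not depend on genetic type. Cause-specific hazard ratios from the same censoring also remain valid.

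**What to change.** In Tables 2.13 and 2.14 and Figures 2.3 and 2.4, replace the Kaplan-Meier rates, quartiles and curves with Aalen-Johansen cumulative incidence by type and arm, with 95% confidence intervals and the other type as a competing event. Amend SAP 7.1.5.1 and 11.6.3, and the table and figure titles and footnotes, to say so. Keep censoring of the other type only for hazard ratios, labelled cause-specific. Derive any number needed to treat from the cumulative incidences, or drop that row from these two tables. Keep the crude n (%) row.

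The cost is SAP wording and programming. No new data, visits or participants are needed, and the primary analysis does not change.
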